### Study Overview

The TEAMS study was a cluster randomized, comparative effectiveness trial comparing the effectiveness of TeleCAM and DirectCAM delivered at 43 clinics across Alabama, Mississippi, and Tennessee. There were 40 clinics initially randomized and 3 satellite sites including Cookeville, Ashland City and Mobile were added later. These 3 satellite sites were not randomized as they were close to and were associated with support groups at the existing randomized sites. The satellites sites were recruited to alleviate logistical challenges in throughput around baseline testing after enrollment.

Using the clinics as the units of randomization, our criteria while identifying clinic sites were to minimize the risk of contamination while having enough sites for a cluster randomization, ability to detect a small to moderate effect size, and ability to recruit efficiently. The randomization list was run by a study statistician who was not involved in any participant interaction and intervention delivery. Given the nature of this study design, group assignments were not blinded to participants and study staff involved in the intervention delivery but were blinded to data analysts.

[figure not shown]

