## Sample Size Calculations and Study Power

For the Main study an *a priori* power analysis was conducted based on sample size estimation for longitudinal designs with attrition with at least 30 sites. Based on the conservative power and sample size calculations, the project was powered for a minimum of 533 participants completing the study with an assumption of a 35% attrition rate; therefore, a total estimated sample size of 820 was needed to detect a between group effect. We assumed intent to treat analyses, 80% power, two-sided family-wise error rate of 0.05, intra-class correlation of 0.05, and a correlation of 0.3 among repeated measures. We also assumed an attrition rate of 35% and a small minimally detectable effect size of 0.2. We make a conservative assumption that the correlation between repeated measures would be 0.3. We have four primary and four secondary outcomes and hence the sample size was estimated after accounting for multiple testing and with a type 1 error rate of 0.00625 for each hypothesis test.

[figure not shown]
For the Enhancement study, we assumed ANCOVA with a pre-post correlation of 0.7, 80% power, one-sided test with statistical significance of 0.05, and attrition rate of 25%. Further, these sample size calculations assumed a non-inferiority margin of -4 units for MFIS, where fatigue is one our key primary outcome identified by the stakeholders in our project. A change of 4 or greater has been found clinically meaningful for quality of life. Based on these assumptions a sample size of 55 completers in rDirectCAM were needed and with an attrition

rate of 25%, we needed 74 participants in rDirectCAM.

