## Analytical and Statistical Approaches

### **Main Study**

Our analysis was following ITT protocol as all participants assigned to the randomized clinics and completed baseline assessment were included in the analysis.

Our primary hypotheses were about comparing the change in the 11 outcomes (listed in **Table 4**) between baseline and 12th month follow-up across the two arms. We considered these 11 hypothesis tests for the 11 outcome variables as part of a single family of hypotheses. We employed the Holm-Bonferroni method for controlling the overall family wise error rate and computed adjusted *p*-values. For each outcome we used a linear mixed effects model, with TeleCAM arm as the reference category, and accounting for the correlated nature of the data due to the nesting of participants within a clinic as random effects. Crude models included fixed effects included both Arms (TeleCAM, DirectCAM), Time (baseline [reference], 3 month, 6 month, 12 month), an Arms X Time interaction, and accounted for randomization strata (clinic location being urban vs. non-urban). The interaction of Arms and Time variables was the primary effect of interest since it quantified the differences within Arm change in the outcome from baseline over time of the two Arms. For example, based on the fitted model that included the interaction between Arm and Time, the difference in change over time from baseline to 12 months between DirectCAM and TeleCAM were estimated. Contrast statements were used to test the null hypotheses in conjunction with the fitted model coefficients and standardized differences in the average treatment effect reported. The estimates of the change in health and function outcomes for each arm and their 95% confidence interval were also reported. As a sensitivity analysis, similar models additionally adjusted for sex, race, and post-COVID data collection measure indicated were also ran. Note that, since post-COVID, data collection for patient reported outcomes was conducted remotely for remaining participants, the former was also included as a covariate in the adjusted model. Next, missingness in primary and secondary outcomes were addressed using multiple imputation technique (MCMC) via PROC MI in SAS,

assuming missing at random. Additional sensitivity analyses were conducted using wild bootstrap to assess the robustness to model assumptions.

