The estimated changes between groups and within groups were then compared to minimally clinically important difference (MCID) published in literature for the studied outcomes among people with MS. For primary outcomes, the published MCID was for MFIS= 4 and SF-36 pain score = 4.9. For secondary outcomes, MCID for 6MWT= 21.56, BBS= 3, TUG= 10.6, FTSTS= 13 and grip strength= 10.5. For exploratory outcomes, MCID was published for SF-36 physical functioning (MCID= 7.1).

Aim 2 was about evaluating pre-specified confirmatory HTE analyses by testing the role of 4 prespecified moderators (age, geographic location/residence based on participants zip codes, type of MS and severity of MS) on each of the primary self-reported outcomes: MFIS, SF-36 MCS, SF-36 PCS, SF-36 pain domain scale, and GLTEQ. We had 4 families of hypothesis tests within this aim – one for every moderator with 2 levels (PDDS 0-3 [without assistive devices] and PDDS 4-7 [with assistive devices]). Our model was like the one used in the primary aim except that we augmented the model with an additional two-way interaction term between moderator (e.g., education level) and Arm (moderator X Arm), and a 3-way interaction term between moderator x Arm x Time. When a 3-way interaction was observed, post-hoc tests were performed to determine the differential influence of the moderator to one treatment versus another, controlling for family-wise error utilizing the Holm-Bonferroni method. We expected no greater than 11 post-hoc tests per pre-specified moderator and used contrast statements to achieve this. Our missing data strategy was similar to that in the primary aim.

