We examined the role of SCT construct variables (social support, outcome expectancies, self-efficacy, self-regulation) as mediating variables between the intervention and primary outcomes. As part of our tertiary aims, we had 4 families of hypotheses, one for each mediating variable listed in **Table 4**. Each family of hypotheses had 5 hypotheses tests, one for each primary outcome. We applied the product of coefficients test framework as our primary approach to compute the mediated effects for each of the primary outcomes as suggested by MacKinnon. Additionally, we did mediation analysis for the 6 secondary and the 7 exploratory outcomes. Note that these analyses were conducted using multiple imputed datasets created for aim 1 sensitivity analyses.

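### If the PROC MI imputation leaves clinic out, the imputed analyses understate between-clinic variance; multilevel imputation should replace it

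*Combined protocol and SAP*

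**What the plan says.** Under Analytical and Statistical Approaches, Main Study, the plan states that "missingness in primary and secondary outcomes were addressed using multiple imputation technique (MCMC) via PROC MI in SAS", assuming missing at random. It does not list the variables in the imputation model, so it says neither that clinic was included nor that it was left out.

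The same section fits a linear mixed model to each outcome, "accounting for the correlated nature of the data due to the nesting of participants within a clinic as random effects". On the target it says: "The interaction of Arms and Time variables was the primary effect of interest". In practice this is the difference between arms in change from baseline to month 12.

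The imputed data are used in three places:
- **Aim 1.** They form a sensitivity analysis beside the mixed model.
- **Mediation.** The plan notes that "these analyses were conducted using multiple imputed datasets created for aim 1 sensitivity analyses".
- **Aim 2 (moderators).** "Our missing data strategy was similar to that in the primary aim".

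Study Overview makes clinics the units of randomisation: "There were 40 clinics initially randomized". Sample Size Calculations and Study Power assumes an "intra-class correlation of 0.05", a repeated-measures correlation of 0.3 and 35% attrition, "with at least 30 sites".

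**The concern.** The MCMC option of PROC MI draws missing values from one multivariate normal distribution and treats participants as independent. This is a property of the software, not something the documents state. Clinic can enter only as ordinary indicator variables, and the plan mentions none.

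If clinic is absent, an imputed month-12 value reflects its clinic only as far as the participant's own earlier scores carry it. Clinic means are then pulled together. The analysis model estimates clinic variance from data in which part of that variance has been removed, and Rubin's rules do not put it back. In a cluster-randomised trial the between-clinic variance sets much of the precision of the arm comparison, so standard errors can come out too small.

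At stake is the analysis meant to show robustness to missing data. So are the mediation analyses, for which the plan names no version without imputation: four mediators by five primary outcomes, plus secondary and exploratory outcomes.

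**Working it through.** **The plan's own figures.** 533/(1 − 0.35) = 820 participants, and 0.05/8 = 0.00625 per test; both reproduce. The plan gives no error rate for the imputed analyses, so simulation is needed.

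**Inputs from the documents.** 820 participants, 40 randomised clinics, ICC 0.05, correlation 0.3, four visits, 35% attrition.

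**Assumptions not in the documents.** 1:1 allocation, equal clinic sizes (820/40 = 20.5 on average), and the correlation of a clinic's effect between visits (clinic autocorrelation, CAC), set at 1, 0.8, 0.5 and 0.

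**Why CAC matters.** With total variance 1, the clinic part of a change score has variance 2 × 0.05 × (1 − CAC): 0, 0.02, 0.05 and 0.10 for the four settings. A stable clinic effect cancels. The complete-data standard error (SE) of the change contrast is

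SE² = (4/40) × [0.10(1 − CAC) + 2(0.95 − τ²)/20.5], with τ² = 0.30 − 0.05 × CAC.

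This gives 0.0826, 0.0934, 0.1076 and 0.1278. The simulated model SEs in complete data were 0.0830, 0.0934, 0.1077 and 0.1276, so the simulation behaves as intended.

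**Main simulation.** 2,000 null trials per setting, monotone missing-at-random dropout (about 64% complete at month 12), 20 imputations, Rubin pooling, clinic-level test at two-sided 5%. Sequential Bayesian normal regression stood in for the MCMC model, using arm and earlier outcomes, with or without clinic indicators. Monte Carlo error is √(0.05 × 0.95/2000) ≈ 0.5 points. Shortfall = 1 − model SE/empirical SE.

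Change from baseline to month 12 (the planned contrast):

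| CAC | Complete data, rejection | No clinic: empirical SE | No clinic: model SE | Shortfall | No clinic: rejection | Clinic indicators: rejection |
|---|---|---|---|---|---|---|
| 1 | 5.0% | 0.0977 | 0.0979 | none | 4.3% | 1.1% |
| 0.8 | 5.1% | 0.1084 | 0.1032 | 4.8% | 5.0% | 1.7% |
| 0.5 | 4.5% | 0.1178 | 0.1116 | 5.3% | 5.2% | 2.2% |
| 0 | 4.3% | 0.1333 | 0.1235 | 7.4% | 6.2% | 1.8% |

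Month-12 score alone:

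| CAC | Complete data, rejection | No clinic: empirical SE | No clinic: model SE | Shortfall | No clinic: rejection | Clinic indicators: rejection |
|---|---|---|---|---|---|---|
| 1 | 5.6% | 0.1125 | 0.1019 | 9.4% | 6.9% | 2.0% |
| 0.8 | 4.8% | 0.1100 | 0.1011 | 8.1% | 6.5% | 1.5% |
| 0.5 | 4.8% | 0.1096 | 0.0993 | 9.4% | 6.9% | 1.3% |
| 0 | 5.1% | 0.1085 | 0.0972 | 10.4% | 7.1% | 1.5% |

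At the per-test level of 0.625%, the change contrast imputed without clinic rejected 0.25% to 0.90%.

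**Checks in a simpler set-up** (40 clinics of 20, 35% missing completely at random, ICC 0.05). Rejection for the change contrast at CAC 1, 0.8, 0.5 and 0:
- 1,500 trials, imputing from arm and baseline only: 3.8%, 4.4%, 5.6%, 6.9%.
- 1,000 trials: 3.2%, 4.7%, 5.5%, 6.5%. Here the SE was 0–7% too small for change and 9–10% too small for the month-12 score. Multilevel imputation brought the SE to within about 2% of the empirical value in every setting.

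For the month-12 score, the 1,500-trial check gave SE 0.101 against 0.110 (8% short, 5.7% rejection) at CAC 1, and 0.098 against 0.112 (1 − 0.098/0.112 = 12.5% short, 7.6% rejection) at CAC 0.

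**The case against.** **The plan does not say that clinic was omitted.** This is correct. A reader might infer omission from the choice of PROC MI, but indicators could have been entered, so the finding is conditional. Silence does not make the imputed results safe, though. Without clinic the SE can be too small; with indicators the clinic-level test is strongly conservative.

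**The planned contrast is a change, not a month-12 level.** This also stands. A reader might carry over month-12 results. One such simulation, imputing from arm and baseline only, gave 7.5% rejection at ICC 0.05 and 11.2% at ICC 0.10. Those figures do not describe the Arm-by-Time contrast, and the second uses twice the planning ICC.

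**Aim 1 does not rest on the imputed data.** Correct: the mixed model is the main analysis. A reader might also expect the imputed analysis to look more significant than the mixed model, and the simulations do not show this. With only clinic and participant random intercepts, imputation without clinic rejected 4.8%, 8.6%, 10.9% and 15.2% at CAC 1, 0.8, 0.5 and 0, against 4.6%, 8.6%, 13.4% and 20.3% in complete data. That excess comes from a missing clinic-by-visit term in the analysis model. It is a separate question, which changing the imputation would not settle.

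**In the other direction**, DirectCAM is delivered by clinic therapists after baseline, so clinic effects on change are plausible. If clinic variance arises only after baseline in both arms (assumed 0.05, against individual variance 1), imputation without clinic rejected 7.1% (SE 0.109 against 0.121, 10% short), and complete cases 5.1%. At an assumed 0.10 the rates were 8.7% and 5.3%. With the variance in DirectCAM clinics only, imputation rejected 5.7% and 7.2%. The documents give no figure for this variance, so these results show only a possible range.

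**Conclusion.** The concern holds in conditional form. The named method has no clinic random effect and the plan describes no clinic term. If clinic was left out, between-clinic variance is understated. At ICC 0.05 and about 35% missing:

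- **Month-12 comparison:** SE about 8–10% too small when all earlier visits are used, with rejection about 5–7% at nominal 5%.
- **Planned change contrast:** no effect if clinic effects are stable over time. If a clinic's baseline effect says nothing about its month-12 effect, the SE is about 7% too small and rejection about 6–7%.

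The documents do not support a claim that the main Aim 1 result is compromised. The exposure is the Aim 1 sensitivity analysis, the mediation analyses built on the same datasets, and Aim 2 so far as it was imputed. Mediation and moderator tests were not simulated, so no error rate is claimed for them. Clinic-dependent dropout and unequal clinic sizes were not simulated either, and 35% is the planned attrition, not observed missingness.

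**What to change.** State which variables were in the imputation model and whether clinic was one of them. Replace the single-level imputation with a multilevel one that has a clinic random effect, lets clinic effects differ by visit, and includes arm and all earlier visits. R, already listed under Data Collection and Sources, can do this. Rerun the imputed Aim 1 analyses, the mediation analyses and any imputed Aim 2 analyses on the new datasets, and report the Aim 1 result beside the mixed model.

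Do not substitute clinic indicators in PROC MI. At this ICC they overstate clinic variance: at CAC 1 the model SE of the change contrast was 0.1206 against an empirical 0.0985, about 22% too large.

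The cost is some code, longer run time, a paragraph of SAP text and slightly wider intervals.

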## **Participants**

The study population included people with MS in the states of Alabama, Mississippi, and Tennessee. Interested participants were enrolled if they self-reported a diagnosis of MS, with a PDDS score between 0 and 7. The PDDS is an ordinal scale ranging from 0 (Normal) to 8 (Bedridden). It is a simple and practical tool for measuring self-reported disability status for people with MS and has a strong correlation ( $rs=0.8$ ) with the Expanded Disability Status Scale (EDSS). Additional inclusion criteria included ages of 18 to 70 years, able to use arms and legs for exercise, and physician clearance. Exclusion criteria included: 1) significantly impaired acuity that prevented seeing a tablet screen to follow home exercise program; 2) cardiovascular disease event within the past six months, severe pulmonary disease, renal failure; 3) active pressure ulcer; 4) currently pregnant; 5) within 30 days of receiving an exercise or rehabilitation program; 6) Godin Leisure Time Exercise Questionnaire (GLTEQ) score  $\geq 24$ .

The GLTEQ contains two questions. The first question asks participants to report weekly frequencies of activities they perform at different intensities. A total weekly leisure activity is a sum of activity scores calculated by multiplying the weekly frequencies of strenuous, moderate, and light activities by 9, 5, and 3, respectively. The second question asks participants the

frequency of weekly leisure-time activities performed that are long enough to work up a sweat.

The scale has been validated and used in previous research with people with MS.

Adverse events (AEs) were monitored following types defined by the Behavior Change Consortium of the National Institutes of Health, which included: falls, cardiovascular-related episodes, musculoskeletal-related events and health care use. The study was approved by the Institutional Review Board of the institution and was conducted in accordance with a clinical trial protocol registered at ClinicalTrials.gov.

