### Interventions and Comparators or Controls

The two study arms received the same CAM intervention, and the comparison was between the on-site delivery (DirectCAM) versus the asynchronous delivery (TeleCAM). The CAM intervention is a 12 week intervention (3 month) composed of 20 sessions that were structured into two segments: the first 8 weeks consisted of two 1-hour sessions per week that included 3 components: 20-minute yoga exercise routine; 20-minute Pilates exercise routine; and a 20-minute routine of dual tasking and functional exercises that involved multifaceted training such as multidirectional upper extremity reaching while carrying on a conversation, and ball bouncing while tracking the ball with head and eye movements. From weeks 9 to 12, the intervention transitioned to one session per week that focused on yoga and Pilates. The intervention was adapted and tailored toward the functional level of each participant, determined by the time it took for participants to complete the Timed 25-Foot Walk (T25FW) test. There were 4 functional levels provided. A participant who had a T25FW score of less than 6 seconds was assigned to TEAMS 1, a T25FW score of 6 to 7.99 seconds was

TEAMS 2, a T25FW score of more than 8 seconds was TEAMS 3, and if unable to complete the T25FW, TEAMS 4 was assigned. If the participant self-reported a diagnosis of osteoporosis and was able to complete the T25FW, they were assigned to TEAMS 3-OP. Those with a diagnosis of osteoporosis that were unable to complete the T25FW were assigned to TEAMS 4-OP. TEAMS 1 and TEAMS 2 completed the intervention exercises in prone, supine, long sitting, standing, and quadriped. TEAMS 3 and TEAMS 3-OP completed the exercises in a chair and with an assistive device for support in standing. TEAMS 4 and TEAMS 4-OP completed all the exercises in a chair. All TEAMS levels included ways to tailor the exercises to better align each participant's functional level. **Figure 2** demonstrates examples of the exercises and adaptation of the CAM intervention.

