**TeleCAM.** The TeleCAM participants received the same intervention content as DirectCAM. The only difference was that the TeleCAM participants received the intervention via exercise videos preloaded to a tablet that was given to them upon enrolling in the study. The exercise videos were filmed with a person with MS instructing and demonstrating the CAM program. Each TeleCAM participant began with one onsite training session with a study therapist. In the training session, participants were shown how to turn the tablet on and off to watch the videos, perform the basic exercises correctly, and use the yoga and Pilates equipment. Participants were asked to bring a family member or friend with them in case they needed assistance using the tablet. The TeleCAM participants were contacted by an Interactive Voice Response (IVR) system-initiated call at their preferred dates and times (aligned with the general intervention timeline) to promote adherence to the yoga/Pilates exercise and neurorehabilitation practice. The IVR system is an automated communication system that includes computers, specialized phone hardware, and operating software to allow immediate computer-assisted interaction with participants by telephone. It was developed during our research team's past physical activity research and in the current study was adapted to address the specific concerns of individuals with MS (physical activity progress, pain, fatigue, and key motivational variables from the SCT). The IVR calls were sent to only

TeleCAM participants weekly for the first six months, and then biweekly for months 6-12 to monitor physical activity, pain, fatigue, and quality of life for SCT variables.

**rDirectCAM.** The rDirectCAM was developed in response to the Covid-19 pandemic and was the Enhancement study intervention. Participants enrolled in rDirectCAM received the same intervention as DirectCAM. The only difference was that the rDirectCAM participants utilized a remote platform at home to work synchronously with a therapist.

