## Time Frame for the Study

For the Main study, TEAMS launched its participant recruitment in October 2017 and ended participant enrollment in 2019. **Figure 4** shows the timeline for a few of the major milestones completed during the study period. Recruitment for the rDirectCAM group (Enhancement study) was not necessary as we had interested participants who already signed up the study via our website or through our clinic partners but were not able to enroll before the Main study needing to be ceased due to the pandemic. We established a protocol for conducting the teleassessments and tele-training and developed a structured set of procedures for equipment purchase and shipping/scheduling based on the Enhancement supplement received in May 2020. We began participant screening for the Enhancement study on September 10, 2020, with 100% enrollment completed on March 22, 2021. The study was closed on November 1, 2021.

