#### 3. March 24, 2020

- a. Our stakeholder panel and the research team determined that *meeting physical activity guidelines* should be added to the inclusion/exclusion criteria to ensure that the intervention being delivered was the catalyst for change and not another exercise routine. Therefore, the *Godin Leisure Time Exercise Questionnaire (GLTEQ)* was added to the exclusion criteria and a GLTEQ score  $\geq 24$  was used as an indicator of individuals meeting physical activity guidelines during the screening process. This addition was approved by our IRB on July 25, 2017.
- b. The EDSS (1-7) was changed to PDDS (0-7) as an inclusion criterion. The rationale for this change was discussed with our stakeholder panel and research team upon realization that very few people with MS knew their EDSS score. This change was approved by our IRB on July 25, 2017.
- c. To honor our commitment to participants enrolled in the study and provide them with the intervention and follow-up assessments remotely during Covid-19, we requested approval for the following modifications:
  - i. Contacted all therapists and participants to suspend onsite visits and requested their participation in completing the intervention (rDirectCAM) and/or performing all testing remotely (teleassessment).
  - ii. The following steps were followed for offering rDirectCAM to participants:
    - For those enrolled in DirectCAM who had started the Intervention (n=25):

- Sent participants a tablet with access to a Zoom link for rDirectCAM.
- Trained therapists to deliver rDirectCAM remotely through the Zoom platform.
- For participants who did not have internet access, we offered a phone call option in which the therapist went through the exercises with the participants via phone, utilized the provided DirectCAM booklet (e.g., “Ok. Now turn to page 3 and let’s do the Warrior pose.”)

4. August 20, 2022

- a. The Covid-19 Enhancement study was added into the research plan.

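### Each arm's uncontrolled change from baseline is compared with published MCIDs, and the between-arm comparison with the MCID has no confidence-interval rule

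*Combined protocol and SAP*

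**What the plan says.** Under Analytical and Statistical Approaches (Main Study), the effect of primary interest is the Arm x Time interaction, that is, the between-arm difference in change from baseline. Each arm's own change is also reported with a 95% confidence interval. The section then adds: "The estimated changes between groups and within groups were then compared to minimally clinically important difference (MCID) published in literature". MCIDs are listed for MFIS (4), SF-36 pain (4.9), 6MWT (21.56), BBS (3), TUG (10.6), FTSTS (13), grip strength (10.5) and SF-36 physical functioning (7.1). None is listed for GLTEQ, PCS or MCS.

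Interventions and Comparators or Controls states: "The two study arms received the same CAM intervention". The later remote arm is active too: "Participants enrolled in rDirectCAM received the same intervention as DirectCAM". No arm is untreated or on usual care.

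Participants excludes people with a GLTEQ score of 24 or more. The change log (item 3a) gives the reason: "to ensure that the intervention being delivered was the catalyst for change and not another exercise routine". GLTEQ is also the physical activity outcome.

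**The concern.** An MCID is a threshold for clinical importance. Setting one arm's change against it invites a statement about whether CAM helped, and this trial has no reference from which to make that statement. The plan has no sentence warning against that reading.

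The second gap is in the between-arm comparison. The MCID is set against the estimated difference, and no rule brings in its confidence interval. A small but imprecise difference between DirectCAM and TeleCAM could then be read as unimportant while the data still allow an important one. Statements of clinical importance are what a reader choosing between delivery modes will use.

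**Working it through.** **1. What the design identifies.** Write the mean change in an arm as d + s, where d is the CAM effect under that delivery mode and s is everything else. The within-arm change estimates d + s. If s is common to both arms, the between-arm difference estimates d(Direct) − d(Tele), and s cancels. With no untreated arm, d and s cannot be separated.

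**2. Possible sources of s in the documents.**
- Study Overview: participants were not blinded. Study Outcomes: the primary outcomes are self-reported. Expectation can therefore enter.
- Table 3: 6MWT, TUG, FTSTS and BBS are repeated at baseline and months 3, 6 and 12. Retest learning is possible on tests that have an MCID.
- Follow-up runs for 12 months in MS, so disease course contributes.
- After COVID, the remaining patient-reported data were collected remotely. The covariate for this appears only in the adjusted sensitivity model.

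The documents give neither size nor direction for any of these. Disease course and the pandemic could worsen scores as well as improve them.

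**3. How often s alone would meet the MFIS threshold.** From the documents: 533 completers (about 266 per arm), repeat correlation ρ = 0.3, MCID 4. Assumed: MFIS SD 15 to 20, no CAM effect, no clustering.

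SE of one arm's mean change = SD × √(2(1 − ρ)/n). For SD 15: 15 × √(1.4/266) = 1.09. For SD 20: 1.45.

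Probability that the arm's mean improvement is at least 4 = Φ((s − 4)/SE):

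| Assumed s (points) | SD 15 | SD 20 |
|---|---|---|
| 2 | 3% | 8% |
| 4 | 50% | 50% |
| 5 | 82% | 75% |

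A simulation of 4,000 trials per setting agreed: 2.7% and 8.8% at 2 points, about 50% at 4, and 82.5% and 75.2% at 5. The expected between-arm difference was zero throughout.

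**4. Precision of the between-arm MFIS difference.** Assumed: 533 completers split equally, SD 15 to 20, ρ from 0.3 (the plan's value) to 0.7, and a design effect (DE) of 1 to 1.6. The upper DE uses the plan's ICC of 0.05 and 40 clinics: 1 + (533/40 − 1) × 0.05 = 1.62. It is an upper bound to the extent that clinic effects cancel in change scores.

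95% half-width = 1.96 × √(8 × SD² × (1 − ρ) × DE/533):

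| SD | ρ | DE 1 | DE 1.6 |
|---|---|---|---|
| 15 | 0.7 | 2.0 | 2.5 |
| 15 | 0.3 | 3.0 | 3.8 |
| 20 | 0.7 | 2.6 | 3.3 |
| 20 | 0.3 | 4.0 | 5.1 |

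An estimate of 2 points has an interval reaching about 4 or beyond in every cell. An estimate of 1 point does so in five of the eight (half-width about 3 or more).

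**5. Secondary note on GLTEQ.** The entry cap covers the whole cohort: "This addition was approved by our IRB on July 25, 2017", and "TEAMS launched its participant recruitment in October 2017". Selecting on a low score makes the mean rise on re-measurement if the screening score is itself the baseline. If Month 0 is a separate measurement, equally correlated with screening as the follow-up is, the selected group's expected baseline and follow-up scores are equal and no artificial rise appears. Tables 3 and 5 schedule a baseline assessment, but the documents do not say whether the screening GLTEQ was reused for it.

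**The case against.** The strongest reply is that the plan contains no decision rule to attack. It says the changes were compared with MCIDs. It does not say that passing one shows efficacy or that falling short shows no important difference. The inferential weight is on the Arm x Time contrast with Holm adjustment, each arm's change comes with an interval, and a sensitivity model adjusts for post-COVID data collection. This stands in part: the plan does not commit to a wrong conclusion, so the supportable claim is that the comparison could be misread. But neither an interval for an arm's change nor a covariate for collection mode supplies an untreated reference.

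A reader might also infer that the low-activity entry rule would itself push outcomes past an MCID. The documents do not support that. GLTEQ, the selected variable, has no listed MCID, and any direct regression to the mean needs the unstated premise that screening served as baseline. For MFIS the effect would be indirect: SD × r × (1 − ρ) × φ(k)/Φ(k), where k is the cap in SD units. With SD 15 to 20, an assumed GLTEQ–MFIS correlation r of 0.2 to 0.4, 50% to 90% of the source population under the cap, and ρ of 0.3 to 0.7, this gives 0.2 to 4.5 points. It reaches 4 only at the extreme corner. Nor does the stated reason for the cap, ruling out another exercise routine, conflict with this: regression to the mean is a separate issue.

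Finally, a whole-interval rule may look like an equivalence framework imposed on a trial powered to detect a difference. That is fair as a limit on scope. The rule is needed only where the report wants to say that an important difference is excluded, and it changes no test.

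**Conclusion.** The point holds in a limited form. Within-arm changes are compared with MCIDs, no arm is untreated, and the plan carries no caveat, so a clinical-importance statement about a single arm cannot be attributed to CAM. The direction of error is open: the uncontrolled part could mimic a benefit or mask one. The between-arm comparison with the MCID lacks an interval rule, and on the assumed inputs the MFIS interval is wide enough for that to matter.

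The sizes above are illustrations. The documents give no MFIS SD and no non-treatment shift, so the probabilities depend on assumed values, and the ρ of 0.3 is the plan's own conservative planning figure. Nothing shows that retest learning would approach the listed thresholds for the timed tests.

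A reader might go further and infer that the primary result is biased or that the trial will claim CAM efficacy. Neither follows. Shifts common to both arms cancel in the Arm x Time contrast, and the text stops at a comparison. The flaw lies in a supplementary interpretation and is cheap to repair.

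**What to change.** In the MCID paragraph of the Main Study analysis section:

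1. Apply the MCIDs to the 95% confidence interval of the between-arm difference in change. Do not state that a clinically important difference is excluded unless the whole interval lies inside ±MCID.
2. Remove the within-group comparison with MCIDs. Report each arm's change with its 95% confidence interval as descriptive, with a sentence saying that it is uncontrolled and cannot be attributed to CAM.
3. For GLTEQ, use the Month 0 score as baseline where it is separate from screening. State which score was used, and disclose that the within-arm rise may include regression to the mean if screening served as baseline.

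The cost is wording in the SAP and the report, with no new data and no change in sample size. The downside is fewer favourable statements about each arm and more inconclusive statements on clinical importance. Where the half-width exceeds the MCID, as in the least favourable MFIS settings above, exclusion of an important difference could not be claimed at all.
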